9.2.2 Itching and Sleep Score

Itching, observed scratching, and sleep disturbance will be assessed twice each day via eDiary. Patient/caregivers will be instructed to fill in the eDiary every morning and evening for the first 24 weeks and the last 21 days before all the remaining visits to the clinic. There will be no interruption between Visits 11 and 12. Patients participating in the optional extension period will stop eDiary entries at Visit 11. Patients and/or caregivers will be instructed to complete the eDiary in the morning after the patient wakes and in the evening just before the patient goes to sleep.

The eDiary includes Albireo ObsRO and PRO items. Patients <8 years of age will not be asked to complete the Albireo PRO items; only the Albireo ObsRO will be completed by caregivers of patients in this age group. Older patients, ≥8 years of age, will complete the Albireo PRO items and the caregiver will complete the Albireo ObsRO items. The Albireo PRO items assess severity of itch, aspects of sleep disturbance (morning diary only), and tiredness. For patients 8 to 12 years of age, the caregiver will read the Albireo PRO items along with the child and record the child's response. A guide will be provided to the caregivers that provides standardized explanations of the Albireo PRO items, in case the patient is confused or requires clarification about the meaning of a question. The Albireo ObsRO items assess severity of observed scratching, aspects of observed sleep disturbance (morning diary only), and observed signs of tiredness (evening diary only). The Albireo ObsRO and PRO scratching and itch

severity items use 0 to 4 response scales, where each response is distinguished by a unique facial expression, verbal anchor, number, and color code ([Appendix 2](#)).

A daily score AM and PM for the Albireo ObsRO scratching item will be averaged from the 2 ratings for each day. A daily score will be considered missing if both of the daily assessments are missing. A weekly score will be calculated by averaging the daily scratching scores. A weekly score will be considered missing if ≥ 4 out of 7 days a week of data are missing. For AM and PM baseline, a 14-day daily score of AM and PM prior to the first dose of study medication will be averaged as the baseline score.

For AM baseline, a 14-day AM score prior to the first dose of study medication will be averaged as the baseline AM score. The same approach will be used for PM baseline and to calculate a patient-reported itch severity score.

9.2.3 Growth

Growth (height and weight) will be measured by the standardized assessments outlined in the US FDA guidance document, *Orally Inhaled and Intranasal Corticosteroids: Evaluation of the Effects on Growth in Children* (March 2007). Height and length (velocity) will be measured using a certified stadiometer and weight (Z-score) using a certified weight scale.

Mid-arm circumference (3 repeat measurements) will be collected at the study site.

Study sites will be trained on using a standardized approach when measuring height with a stadiometer and additional detailed instructions will be provided in study documents.

BMI will be calculated by weight (kg) / height (m)². Change will be defined as linear growth deficit (weight and BMI for age) compared to a standard growth curve.

9.2.4 Biomarker Samples

Blood samples for p-C4 and autotaxin will be drawn at Visits 1, 2, 5, 8, and 11 (p-C4 and autotaxin will only be drawn for patients with body weight >10 kg). Samples will be treated and transported to a central laboratory per instructions in the laboratory manual.

9.2.5 Change of Antipruritic Medication

Any change of antipruritic medication must be noted in the eCRF.

9.2.6 Quality of Life Questionnaire (PedsQL)

Caregivers and, if applicable, patients will be asked to fill out a QoL questionnaire (PedsQL) at Visits 1, 5, 8, 11 and at all visits of the optional extension period. Details of the questions included on the questionnaire can be found in [Appendix 4](#).

9.2.7 PELD/MELD Score

The PELD score will be calculated for children up to 12 years of age. For patients 13 years or older, the MELD score will be calculated.

PELD Score = $4.80 * \ln(\text{total bilirubin}) + 18.57 * \ln(\text{INR}) - 6.87 * \ln(\text{albumin}) + 4.36$ (if patient <1 year: scores for patients listed for liver transplantation before the patient's first birthday continue to include the value assigned for age (<1 year) until the patient reaches the age of 24 months) + 6.67 (if patient has growth failure [<-2 SD])

Laboratory values less than 1.0 will be set to 1.0 for the calculation of the PELD score.

MELD Score = $9.57 * \ln(\text{creatinine}) + 3.78 * \ln(\text{total bilirubin}) + 11.2 * \ln(\text{INR}) + 6.43$

Laboratory values less than 1.0 will be set to 1.0 and serum creatinine values greater than 4.0 mg/dL (equivalent to 353.6 $\mu\text{mol/L}$) will be set to 4.0 for calculation of the MELD score.

If a patient goes from 11 years of age to 12 between the beginning and end of study, both PELD and MELD scores will be calculated at the first visit after the 12th birthday and move to MELD score. The results should be displayed in one summary table.

9.2.8 Fibroscan®

Where available, Fibroscan® will be performed as per institution standard practice at Visits 1, 5, 8, and 11.

9.2.9 Markers of Fibrosis

APRI score and Fib-4 score will be calculated at Visits 1, 3, 5, 8, and 11.

APRI = $[(\text{AST in U/L}) / (\text{AST upper limit of normal [ULN] in U/L})] \times 100 / (\text{Platelets in } 10^9/\text{L})$

Fibrosis 4 Score = $(\text{Age} * \text{AST in U/L}) / (\text{Platelets in } 10^9/\text{L} * \sqrt{(\text{ALT in U/L})})$

9.2.10 Liver Biopsy

If a liver biopsy is performed according to the local regulations or standard of care at any time during A4250-008, the biopsy results should be recorded in the eCRF. If the patient has liver biopsy results collected in study A4250-005 or prior to Week 24 in study A4250-008, the patient will be asked to consent to a follow up liver biopsy, if allowed per local regulations, at Visit 11 unless 2 prior liver biopsy results have been collected with at least 1 year between biopsies. Liver biopsies will not be performed in Spain.

9.2.11 Global Impression of Change and Global Impression of Symptom Measures

Patients, caregivers, and clinicians will complete the PGIC and the PGIS measures at Visits 1, 2, 3, 5, 8, 11, and at all visits of the optional extension period ([Appendix 3](#)).

The PGIC items assess change in itch (patient version), scratching (caregiver and clinician versions), and sleep (all versions) since starting the study drug. The PGIS items assess itch (patient version), scratching (caregiver and clinician versions), and sleep (all versions) in the past week. Caregivers and clinicians will complete the PGIC and PGIS for all patients; those patients ≥ 8 years of age will complete the patient version.

10 ASSESSMENT OF SAFETY

The timing and frequency of safety assessments are described in [Section 7.1.2](#) and [Section 7.1.3](#).

The primary safety analysis for this study will include the incidence of total treatment-emergent adverse events (TEAE) and TEAEs categorized by causality, severity, and seriousness assessments.

Trends in safety will also be evaluated for the following assessments:

- Physical examinations
- Concomitant medications
- Vital signs
- Laboratory test results (including clinical chemistry, hematology, urinalysis, AFP, vitamins A, E, and 25-hydroxy vitamin D, and INR)
- Abdominal ultrasound
- Discontinuations due to AEs

10.1 Adverse Events

10.1.1 Definitions and Investigator Assessments

An AE is defined as any untoward medical occurrence in an enrolled patient regardless of causal relationship with study drug. An AE can therefore be any clinically significant unfavorable and unintended sign, symptom, or disease that occurs once a patient is enrolled (ICF is signed) in the study until the patient is discharged from the study, whether or not related to the study drug.

10.1.1.1 Clinical Significance

Clinical significance is defined as any abnormal finding that results in further clinical investigation(s), treatment(s), or the diagnosis of new condition. Patient-reported events and protocol-mandated laboratory values, vital signs, and physical examination findings can be considered clinically significant (i.e., an AE) if there is a deterioration as compared to baseline. Examples of clinically significant worsening from baseline could include, but is not limited to, events causing withdrawal from the study and events requiring medical intervention outside of the study causing apparent clinical manifestations, or judged relevant by the investigator.

10.1.1.2 Serious Adverse Events

Serious criteria are applied by the investigator to each AE as specifically defined below. These criteria are used to determine whether an AE is serious or non-serious. The assessment is made independently of severity assessment ([Section 10.1.1.3](#)). For example, the development of a

severe rash that occurs after signing of informed consent may not meet serious criteria as defined below and therefore would be considered a severe, non-serious AE.

Any AE that meets any 1 of the following 6 criteria is considered an SAE:

- The outcome of the AE is **death**
- The AE is immediately **life-threatening**. Life-threatening means that the patient is, in the opinion of the investigator, at immediate risk of death from the reaction as it occurred. This does not include an AE that, if more severe, might have caused death
- The AE results in persistent or significant **disability/incapacity**. Disability means a substantial disruption of a person's ability to conduct normal life functions
- The AE requires or prolongs **hospitalization**
- The AE results in a **congenital anomaly/birth defect**
- **The AE is an important medical event.** Important medical events may meet serious criteria should the investigator assess that they may significantly jeopardize the patient, represent a significant hazard, or requires medical/surgical intervention to prevent one of the outcomes listed above. Examples of potential SAEs based on this criterium include, but are not limited to, allergic bronchospasm requiring intensive treatment in an emergency room or at home, blood dyscrasias or convulsions even if they do not result in inpatient hospitalization, or the development of drug dependency and drug abuse.

10.1.1.3 Severity Assessment

Severity assessments are based on the intensity of the event in relation to expectation. The investigator will assess the intensity of AEs based on the following definitions:

- Mild (awareness of sign or symptom, but easily tolerated)
- Moderate (discomfort sufficient to cause interference with normal activities)
- Severe (incapacitating, with inability to perform normal activities)

Severity is a measure of intensity where seriousness is defined by the criteria outlined in **Section 10.1.1.2**. An AE of severe intensity need not necessarily be considered serious. For example, nausea that persists for several hours may be considered severe nausea, but not meet serious criteria, and therefore would be assessed as a severe AE but not an SAE.

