In a Phase 3 randomized double-blind study in children with PFIC, treatment with A4250 at doses of 40 and 120 µg/kg/day led to statistically significant reductions in serum bile acid levels and pruritus symptoms over 24 weeks compared with placebo (study A4250-005; PEDFIC 1). These improvements occurred rapidly and were sustained during continued treatment. Results for secondary and exploratory endpoints were generally consistent with the reductions in serum bile acids and pruritus showing improvements in sleep, hepatic biochemical parameters and hepatic health, and quality of life (QoL) measures.

A4250 has been generally well tolerated in all completed studies. Adverse events (AEs) reported have primarily been of mild to moderate intensity. In total, 6 serious adverse events (SAEs) have been reported; none judged by the investigator to be causally related to the study drug. No deaths related to the drug have been reported. Abdominal pain and diarrhea have been the most prominent AEs in adults, while diarrhea, pyrexia, and upper respiratory tract infection have been the most commonly reported AEs in children. The most commonly reported study drug-related AEs in children were increases in alanine aminotransferase (ALT), aspartate aminotransferase (AST), and blood bilirubin.

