10.2.2 Individual Patient Safety Monitoring

10.2.2.1 Liver Monitoring

Strategies to monitor markers of liver disease throughout the study are outlined below where the ULN will be based on central laboratory reference values for age and gender.

For abnormalities classified as hepatic adverse events and/or hepatic decompensation, a PK sample should be collected as close to the onset of the event as possible (PK samples are not required during the screening period).

If isolated transaminase elevations are observed, defined as:

1. Normal bilirubin AND absence of clinical hepatitis symptoms AND
 - ALT or AST $\geq 5 \times$ ULN (if normal at baseline) or an absolute threshold of 800 U/L, whichever comes first
 - OR ALT or AST $\geq 3 \times$ baseline (if abnormal at baseline) or an absolute threshold of 800 U/L, whichever comes first

Then:

- a) Repeat liver profile (AST, ALT, bilirubin, and prothrombin time [PT] or INR) within 2 to 3 days
- b) Evaluate creatine phosphokinase (CPK) and lactate dehydrogenase (LDH)
- c) As needed (for example, persistent ALT/total bilirubin elevation or worsening of liver function), consider evaluation for alternative etiologies

Monitor the patient using close observation found in [Section 10.2.2.2](#).

If any ONE of the following criteria are met:

1. Transaminases (ALT or AST $\geq 3 \times$ baseline or absolute threshold increase of +300 U/L, whichever comes first) AND bilirubin increases to such where total bilirubin $> 2 \times$ ULN if total bilirubin was within normal range at baseline
2. Transaminase elevations alone (ALT or AST $> 5 \times$ ULN for patients that were normal at baseline) or absolute threshold of +300 U/L (for patients starting with transaminases above ULN at baseline) in presence of normal LDH and CPK
3. Total bilirubin increased, unrelated to hemolysis (elevated reticulocyte count) or established genetic diseases, such as Gilbert's syndrome
 - a) Doubling if total bilirubin was < 3 mg/dL (equivalent to 51.3 μ mol/L) at baseline and total bilirubin is greater than 2 x ULN
 - b) OR Increase by > 3 mg/dL (equivalent to 51.3 μ mol/L) if total bilirubin was ≥ 3 mg/dL (equivalent to 51.3 μ mol/L) at baseline
4. INR increase refractory to vitamin K administration
 - a) Increase by > 1.5 if INR was normal at baseline
 - b) OR Increase by > 0.4 if INR was abnormal at baseline

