11.2.2.7 Evaluation of Safety Variables

Safety data will be analyzed using descriptive statistics and summaries overall of SAEs, AEs, vital signs, clinical laboratory tests (hematology, clinical chemistry and urinalysis) and concomitant medication. Analyses will be performed using the full analysis set.

Summaries of AEs (coded according to the Medical Dictionary for Regulatory Activities (MedDRA) system organ class and MedDRA preferred term) will include:

- Overview of the incidence of TEAEs (TEAEs, Drug-related TEAEs, TEAEs leading to study discontinuation, and Treatment-emergent SAEs)
- TEAEs by system organ class (SOC) and preferred term
- Intensity of TEAEs by SOC and preferred term
- Drug-related TEAEs by SOC and preferred term
- TEAEs leading to study discontinuation by SOC and preferred term
- Treatment-emergent SAEs by SOC and preferred term

Concomitant medication use during the Treatment Period will be summarized by Anatomical Therapeutic Chemical (ATC) class and World Health Organization (WHO) preferred name.

Summaries of vital signs will be presented. For each visit, the actual results and the change from baseline, and the number and percentage of patients with potentially clinically significant (PCS) values observed post-baseline will be presented.

Summaries of clinical safety laboratory data will be presented. For each visit, the actual result and the change from baseline, and the number and percentage of patients with PCS values observed post-baseline will be presented.

Data listings will be provided for each patient for all safety parameters.

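### The only AE severity scale rests on symptoms and function, so the severity tables cannot separate small from large ALT, AST and bilirubin rises

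*Protocol*

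**What the plan says.** Protocol Section 10.1.1.3 sets out three levels: "Mild (awareness of sign or symptom, but easily tolerated", "Moderate (discomfort sufficient to cause interference with normal activities" and "Severe (incapacitating, with inability to perform normal activities". It opens with a general rule: "Severity assessments are based on the intensity of the event in relation to expectation".

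Section 10.1.2 has the investigator record severity on this basis for all AEs, and Section 10.1.1.1 allows a laboratory value that has worsened from baseline to be an AE. The protocol contains no other severity scale and no rule for grading laboratory AEs.

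On the expected toxicity, Section 5.2.2 reports: "The most commonly reported study drug-related AEs in children were increases in alanine aminotransferase (ALT), aspartate aminotransferase (AST), and blood bilirubin". Section 10.2.2.1 describes isolated transaminase elevations, whose definition begins "Normal bilirubin AND absence of clinical hepatitis symptoms AND" and then sets limits in multiples of ULN, multiples of baseline, or 800 U/L. Its second interruption criterion can be met by a transaminase rise with no other liver finding, provided LDH and CPK are normal.

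On reporting, Section 10 includes in the primary safety analysis "TEAEs categorized by causality, severity, and seriousness assessments", and Section 11.2.2.7 plans a table of "Intensity of TEAEs by SOC and preferred term".

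**The concern.** The protocol uses two yardsticks for the same hepatic event. Section 10.2.2.1 ranks it by the laboratory value, and Section 10.1.1.3 ranks it by how the patient feels and functions. For a rise without symptoms the second yardstick carries no information about size, yet it is the one that feeds the severity result.

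A summary that most hepatic TEAEs were mild would then say little about how high the values went. Investigators who do take the value into account have no common cut-points, so the same ALT can be graded differently at different sites. With up to 50 sites and about 120 patients, a few such differences could shift a small table.

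**Working it through.** The protocol states no figure to reproduce here. The check is a comparison of sections, followed by one illustration.

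**1. Does the scale cover laboratory AEs?** Yes. Section 10.1.1.1 admits them as AEs, and Section 10.1.2 grades every AE under Section 10.1.1.

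**2. Where can a symptom-free rise fall?**
- Severe needs incapacity: not met.
- Moderate needs discomfort that interferes with activity: not met.
- Mild needs awareness of a sign or symptom. It is met only if the laboratory finding counts as a sign; otherwise no level fits.
- The opening reference to expectation allows a higher grade by judgment but gives no cut-points.

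The grade is therefore Mild, undefined, or a matter of opinion. None of these depends on the size of the rise in a fixed way.

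**3. Does the protocol expect such rises?** Yes, as a category. Section 10.2.2.1 defines isolated elevations by the absence of hepatitis symptoms, and its second interruption criterion does not require symptoms. An event that leads to interruption need not fit the wording of Moderate or Severe.

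**4. Where does the grade go?** Into the severity breakdown of the primary safety analysis (Section 10) and the intensity table (Section 11.2.2.7).

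**5. Illustration.** The protocol gives no numeric ULN; Section 10.2.2.1 takes it from the central laboratory by age and gender. Assume 30 to 60 U/L.

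| Assumed ULN (U/L) | 5 x ULN (U/L) | 800 / ULN | 800 / (5 x ULN) |
|---|---|---|---|
| 30 | 150 | 26.7 | 5.3 |
| 40 | 200 | 20.0 | 4.0 |
| 50 | 250 | 16.0 | 3.2 |
| 60 | 300 | 13.3 | 2.7 |

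Take two symptom-free patients with normal baseline, one just at 5 x ULN and one at 800 U/L. Their values differ by a factor of 2.7 to 5.3, and the scale offers no wording that tells them apart.

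The 800 U/L figure is an alternative limit that applies only if it is reached first. With normal baseline that needs 5 x ULN above 800, so a ULN above 800 / 5 = 160 U/L. With abnormal baseline it needs 3 x baseline above 800, so a baseline above 800 / 3 = 267 U/L. A normal-baseline patient would thus be flagged at 150 to 300 U/L under the assumed ULN. The multiples of 800 U/L show scale only; they do not estimate bias in any planned result.

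**The case against.** Four points can be made on the other side.

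- **The scale leaves room for judgment.** Severity is judged against expectation, and the hepatitis example in Section 10.1.2 lists raised ALT and AST among signs and symptoms, one of which may be more severe than expected. An investigator may therefore grade a silent rise above Mild. This stands, and it rules out saying that the text forces Mild. It does not supply a common rule, so it turns a fixed low grade into a variable one.
- **The liver signal is reported elsewhere.** Section 11.2.2.7 gives actual results, changes from baseline and counts of potentially clinically significant values by visit, with patient listings. Section 9.1.3 has ALT, GGT and total bilirubin as an exploratory endpoint. Seriousness is judged independently of severity, the interruption rules are numeric, and the DSMB reviews liver values. This stands in full. None of these outputs, however, attaches a size to each TEAE alongside its causality, which is what the severity table is meant to do.
- **A derived grade belongs in the SAP.** The derivation does, and the SAP was not available for this review. The scale applied at data entry and the place of severity in the primary safety analysis are protocol matters. If the SAP already grades laboratory TEAEs by value, only a cross-reference is needed.
- **The study is descriptive.** Section 11.1 says there is no formal hypothesis testing. That limits the consequence to how safety is described, which is the purpose of this table.

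**Conclusion.** The point holds as a weakness in grading and reporting. The protocol fixes one symptom-and-function scale for all AEs and gives no basis for grading laboratory AEs by size, although hepatic laboratory rises are the most commonly reported drug-related AEs in children. Symptom-free rises can be graded Mild or graded inconsistently, so the severity breakdown and the intensity table cannot separate small from large ones.

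Two stronger readings are not supported. A reader might infer that the leading drug-related AEs are asymptomatic. Section 5.2.2 does not say so, and Section 10.2.2.1 foresees symptom-free rises as a category without giving a frequency. A reader might also infer that no such event can be moderate or severe. The reference to expectation leaves that to judgment, and even Mild is not clearly met.

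The number of TEAEs affected cannot be given from the protocol, and the multiples of ULN rest on the assumed 30 to 60 U/L. This is a cheap improvement to the safety report, and it does not mean that a liver signal would be missed.

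**What to change.** Keep the investigator's grade as it is. For laboratory TEAEs, add a second grade computed from the laboratory value on a named, published laboratory toxicity scale:

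- use multiples of ULN when baseline is normal and multiples of baseline when it is abnormal; Section 10.2.2.1 already uses both kinds of reference;
- take the highest value between onset and resolution of the AE, with the central laboratory's ULN for age and gender;
- name the baseline. Section 11.2.2.1 defaults to Baseline 2, which for Cohort 1 patients who received A4250 in Study A4250-005 is already an on-treatment value;
- show the derived grade beside the investigator's grade in the intensity table of Section 11.2.2.7, not in place of it, and in the scale's own grades.

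One sentence in Section 10.1.1.3 should say that laboratory AEs also receive this derived grade, and the SAP should carry the derivation.

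The cost is one derivation and one extra display from values already collected. More hepatic TEAEs will appear at higher grades, and readers will see two scales in one table. Monitoring, interruption and re-challenge rules are untouched.
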